6.4. Medical History

Relevant medical history, including the existence of current signs and symptoms, will be listed by LEAP Trio participant cohort and body system.

7. STUDY OPERATIONS

7.1. Protocol Deviations

Major protocol deviations will be listed with information such as type of deviation, date of occurrence, and the reason for the deviation. Protocol deviations will be summarized in tabular format by type of deviation.

8. ENDPOINT EVALUATION

8.1. Overview of Efficacy Analysis Methods

8.1.1. Assessment Time Windows

Visit 144 is expected to be completed within 8 weeks of enrollment. The visit window does not apply to the telephone visit. Multiple visits may be conducted to complete all assessments for Visit 144. Evaluations collected outside of the visit window for Visit 144 will not be excluded from analyses.

8.1.2. Multiple Comparisons/Multiplicity

No multiplicity adjustments will be applied to the analysis tests conducted for this study.

8.2. Co-Primary Endpoints

For a listing of the co-primary endpoints, see the Protocol Summary in Section 3 above and Section 3.2.1 of the protocol V7.0.

8.2.1. LEAP Participants

The primary endpoint for LEAP Participants is the rate of peanut allergy at Visit 144 (V144).

8.2.1.1. Computation of the Primary Endpoint

Peanut allergy status at V144 will be determined by peanut challenge where possible. Peanut challenges are described in protocol section 6.7. Participants meeting criteria for peanut oral allergy syndrome in the absence of primary peanut allergy as described in protocol section 3.3.5 will not be considered peanut allergic.

Individuals who report consuming at least 2 g of peanut protein without reaction on at least one occasion in the last year will be considered peanut tolerant.

If oral challenge is not possible and participants do not meet the above criteria for tolerance, peanut allergy status will be determined by an internally and externally validated novel peanut allergy prediction model, the manuscript for which is currently in preparation: Developing a Prediction Model for Determination of Peanut Allergy Status in The LEAP Trio Study; Sever ML, Calatroni A, Roberts G, et al. The model was developed using data from the LEAP participants, and incorporates peanut wheal size (mm), peanut specific IgE (kU/L), Ara h1 (kU/L), Ara h2 (kU/L) and Ara h3 (kU/L). The model performs with high level of accuracy, and continues to perform reasonably well in the context of missing blood or skin prick data. This model replaces the previously specified algorithm for determination of peanut allergy status. The V144 assessments with non-missing data will be used as independent variables in the peanut allergy prediction model to impute peanut allergy status. LEAP Participants who do not have an oral food challenge, do not meet the peanut consumption criteria for tolerance and do not have any of the assessments for the peanut allergy prediction model will not be included in the primary analyses of the primary endpoint.

8.2.1.2. Primary Analysis: Between-group comparison

The main comparison for the LEAP Participant primary endpoint is the rate of peanut allergy between LEAP Consumers and LEAP Avoiders at V144 in the ITT population. This comparison will be made by an unadjusted logistic regression model at the 0.05 level of significance. This comparison evaluates whether the consumption of peanut starting in infancy induces long-lasting tolerance to peanut.

The same statistical methodology will be repeated for the LEAP Participants in the PP population.

The same statistical methodology will be repeated in the ITT and PP populations, separately, within each stratum from the LEAP Study randomization (skin prick test (SPT)-positive and SPT-negative groups from the LEAP Study).

Additional logistics regression models will be performed to adjust for potential confounders, such as age, gender, ethnicity, family history and other allergic comorbidities

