## Figure 1. LEAP Screening, Participant, Sibling, and Parent Cohorts

The number of siblings in the Ad Lib section are based on findings in a survey regarding siblings of LEAP participants. These numbers represent an estimate of the total participants expected to enroll.

Participants in the current study derive from participants in previous LEAP trials and their families. The LEAP Screening Cohort has been described. The LEAP study enrolled 640 participants, of whom 556 were also studied in the LEAP-On follow up study. All participants who enrolled in LEAP, including those who were not part of the intent-to-treat (ITT) population, are eligible to enroll in this study. Parents and siblings of LEAP participants who meet other eligibility criteria described in sections 4.2 and 4.3 are eligible to enroll.

We reviewed the ages and dates of enrollment of participants in the LEAP trial. The times of enrollment and participation are shown in Figure 2. We assume the trial opens for enrollment in March 1, 2018. The last day for enrollment is August 31, 2022. The study was extended to accommodate for slowed enrollment due to the COVID-19 pandemic. As a result of the study extension, participants are predicted to be older than originally planned. This difference is not likely to significantly alter the study outcomes, as allergic status is unlikely to change during this time interval. These parameters allow us to describe expected ages at enrollment of LEAP participants in the current study.

Participant A, and similar participants who were relatively old at enrollment and enrolled relatively early in LEAP, could be as old as [10.9 months + (August 31, 2022 - February 2, 2007)] = 332 + 5689 days or 16.5 years.

For participant E, and similar participants who were relatively young at enrollment and enrolled relatively late in LEAP, the minimum age for eligibility applies (section 4.1.1). At the time of trial opening they would be as young as [4.5 months + (March 1, 2018 - March 20, 2009)] = 137 + 2844 days or 9.3 years. The minimum age of 9.5 years for eligibility means such participants could therefore be eligible for enrollment 0.2 years after March 1, 2018, or in May 2018 or after.

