# 9.3 SAMPLE SIZE

# **LEAP Participants**

The sample size is based on the number of children likely to be available to enroll in the study. As shown in the Figure 1 LEAP Screening, Participant and Sibling Cohorts, there are 311 LEAP avoiders and 319 LEAP consumers (total 630) potentially eligible for enrollment. In the LEAP study, the rate of peanut allergy was 3.2% among consumers and 17.2% among avoiders at 60 months of age. We assume that the rates will not change markedly between month 60 and 144. We wish to detect a difference between the groups that are similar to that detected at 60 months. 88.5% of those potentially eligible enrolled in the follow on LEAP-On Study. We assume a lower percentage of those potentially eligible will enroll in this study.

For example, if 80% of those potentially eligible enroll, the true rate of allergy among LEAP consumers at 144 months is 6%, and the true rate of allergy among LEAP avoiders at 144 months is 15%, there is 91% power to detect a difference with a two-sided type I error of 0.05 between the groups. If only 70% enroll and other assumptions remain constant, there would be about 87% power to detect a difference.

Other examples are shown in Figure 3.

Three possible recruitment rates are shown in the left, middle and right panels. In each panel, the power to detect a difference, with a two-sided type I error of 0.05, between groups is shown on the vertical axis for different assumptions regarding the true underlying allergy rates in the consumer and avoider groups at month 144. In each panel contour lines display rates in consumers of 2%, 4%, 6%, 8% and 10% while the horizontal axis displays a range of rates in avoiders of 10 to 25%

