#### 9.5 REPORTING DEVIATIONS FROM THE ORIGINAL STATISTICAL PLAN

The principal features of both the study design and the plan for statistical data analysis are outlined in this protocol and in the SAP. Any change in these features requires either a protocol or an SAP amendment, which is subject to review by the NIAID DSMB, the study sponsor and the Ethics Committee. These changes will be described in the final study report as appropriate.

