6.2. Demographic and Other Baseline Characteristics

Summary descriptive statistics for demographic characteristics collected at Visit 144 will be reported for the enrolled, ITT and PP samples by LEAP Trio participant cohort and treatment arm. Characteristics to be summarized include age, ethnicity, and sex.

Summary descriptive statistics for demographic, baseline, V60 characteristics collected in LEAP, and V72 characteristics collected in LEAP On will be presented by treatment arm for participants who did and did not participate in the LEAP Trio study. Characteristics to be presented include age, ethnicity, sex, skin prick test to peanut, and peanut IgE and its components.

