8.2.1.2.3. Sensitivity Analysis: Imputation of PP population from LEAP PP

LEAP PP Participants who participated in LEAP Trio but have a missing peanut allergy determination for LEAP Trio at V144 according to the definition in section 8.2.1.1, or who did not participate in LEAP Trio will have the peanut allergy status at V144 imputed.

LEAP PP Participants with a missing peanut allergy determination at V144 will have their peanut allergy status from the LEAP On primary endpoint for peanut allergy status at V72 carried forward (via LOCF) as their V144 peanut allergy status. LEAP PP Participants with a missing peanut allergy status at V72 will have their peanut allergy status from the LEAP primary endpoint for peanut allergy status at V60 carried forward (via LOCF) as their V144 peanut allergy status.

The same statistical methodology in section 8.2.1.2 will be repeated for this sensitivity analysis to compare the rate of peanut allergy between LEAP Consumers and LEAP Avoiders at V144.

8.2.1.2.4. Sensitivity Analysis: Imputation of PP population from LEAP PP with Transient Allergy Rate

LEAP PP Participants who participated in LEAP Trio but have a missing peanut allergy determination for LEAP Trio at V144 according to the definition in section 8.2.1.1, or who did not participate in LEAP Trio will have their peanut allergy status at V144 imputed.

LEAP PP Participants with peanut allergy status at V72

For the LEAP Participants with a peanut allergy status at both V72 and V144, if there are any participants whose peanut allergy status changes from V72 to V144, the percentage of participants who change from allergic to tolerant (%A72→T) and the percentage of participants who change from tolerant to allergic (%T72→A) will be calculated.

For LEAP PP Participants with a missing peanut allergy determination at V144 and a peanut allergy status of allergic at V72 (NumPPA72), [NumPPA72 * %A72→T] participants will be randomly selected to be imputed as tolerant at V144 and the remaining participants in NumPPA72 will be imputed as allergic at V144.

For LEAP PP Participants with a missing peanut allergy determination at V144 and a peanut allergy status of tolerant at V72 (NumPPT72), [NumPPT72 * %T72→A] participants will be randomly selected to be imputed as allergic at V144 and the remaining participants in NumPPT72 will be imputed as tolerant at V144.

LEAP PP Participants with missing peanut allergy status at V72

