8.2.1.2.5. Sensitivity Analysis: Imputation of ITT population from LEAP ITT

LEAP ITT Participants who participated in LEAP Trio but have a missing peanut allergy determination for LEAP Trio at V144 according to the definition in section 8.2.1.1, or who did not participate in LEAP Trio will have the peanut allergy status at V144 imputed.

LEAP ITT Participants with a missing peanut allergy determination at V144 will have their peanut allergy status from the LEAP On primary endpoint for peanut allergy status at V72 carried forward (via LOCF) as their V144 peanut allergy status. LEAP ITT Participants with a missing peanut allergy status at V72 will have their peanut allergy status from the LEAP primary endpoint for peanut allergy status at V60 carried forward (via LOCF) as their V144 peanut allergy status.

The same statistical methodology in section 8.2.1.2 will be repeated for this sensitivity analysis to compare the rate of peanut allergy in the LEAP ITT population between LEAP Consumers and LEAP Avoiders at V144.

8.2.1.2.6. Sensitivity Analysis: Imputation of ITT population from LEAP ITT with Transient Allergy Rate

LEAP ITT Participants who participated in LEAP Trio but have a missing peanut allergy determination for LEAP Trio at V144 according to the definition in section 8.2.1.1, or who did not participate in LEAP Trio will have their peanut allergy status at V144 imputed, using the same imputation methods specified in section 8.2.1.2.4.

The same statistical methodology in section 8.2.1.2 will be repeated for this sensitivity analysis to compare the rate of peanut allergy in the LEAP ITT population between LEAP Consumers and LEAP Avoiders at V144.

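### The LEAP-participant co-primary comparison has no planned pooled estimate adjusted for the LEAP randomisation stratum (SPT-positive or SPT-negative)

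*SAP*

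**What the plan says.** SAP 8.2.1.2 defines the main comparison of LEAP Consumers and LEAP Avoiders: "This comparison will be made by an unadjusted logistic regression model at the 0.05 level of significance". Protocol 9.2.1 specifies the same model.

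The SAP then repeats that model, in ITT and PP, "within each stratum from the LEAP Study randomization (skin prick test (SPT)-positive and SPT-negative groups from the LEAP Study". It also plans further adjusted models. The covariates named are age, gender, ethnicity, family history and other allergic comorbidities in the SAP, and age, gender and unspecified others in Protocol 9.2.1. Both lists are open-ended, so the SPT stratum is unnamed, not excluded. The six imputation analyses (SAP 8.2.1.2.1 to 8.2.1.2.6) reuse the 8.2.1.2 methods.

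Two provisions bear on attrition:

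- SAP 6.2 compares children who did and did not join LEAP Trio, by arm: "Characteristics to be presented include age, ethnicity, sex, skin prick test to peanut, and peanut IgE and its components".
- SAP 8.2.1.2.5 and 8.2.1.2.6 impute back to the LEAP ITT population. The first carries V72 or V60 status forward. The second works "using the same imputation methods specified in section 8.2.1.2.4", where the transition rates are defined as: "For the LEAP Participants with a peanut allergy status at both V72 and V144, if there are any participants whose peanut allergy status changes". Neither arm nor stratum is mentioned in that definition.

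**The concern.** The stratum is the one covariate that the LEAP design itself fixed, before any outcome was known. The plan uses it only in a way that yields two separate and less powerful results beside an unadjusted overall one. No pooled estimate uses the design factor.

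Two things are at stake. The first is a little precision. The second is balance. Protocol 9.3 expects a lower share to enrol than the 88.5% who joined LEAP-On and illustrates 80% and 70%. Under SAP 8.2.1.1, children whose status cannot be determined leave the primary analysis. The children analysed are therefore a subset of those randomised, and the strata may no longer be balanced by arm. A model with arm and stratum, standardised to the randomised cohort, corrects loss that depends only on those two factors. It does so without assuming that allergy status at V60 or V72 carries forward.

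A lesser point affects only the additional models. SAP 8.2.1.2 gives no time of measurement for the allergic comorbidities, while SAP Table 2 compares asthma, rhinitis and eczema at V144 by arm as outcomes. Adjusting for V144 values could remove part of the intervention's own effect.

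**Working it through.** **1. The plan's power.** Inputs from Protocol 9.3: 311 avoiders, 319 consumers, 15% against 6%, two-sided 0.05. Enrolment of 80% gives 249 and 255; 70% gives 218 and 223. The formula is power = Φ[(|p1 − p2| − 1.96·SE0)/SE1], with SE0 pooled and SE1 unpooled.

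- 80%: pooled rate = (249 × 0.15 + 255 × 0.06)/504 = 0.1045; SE0 = 0.02725; SE1 = √(0.15 × 0.85/249 + 0.06 × 0.94/255) = 0.02708; (0.09 − 1.96 × 0.02725)/0.02708 = 1.351; power **91.2%** (stated 91%).
- 70%: SE0 = 0.02913; SE1 = 0.02894; (0.09 − 1.96 × 0.02913)/0.02894 = 1.137; power **87.2%** (stated about 87%).

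**2. Assumptions about the stratum.** The documents give neither the SPT-positive share nor rates by stratum. Assumed: share 15-25%, stratum-allergy odds ratio 2-6, a common arm odds ratio, and overall rates held at 15% and 6%. For example, a 20% share and odds ratio 4 imply these rates:

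| | SPT-positive | SPT-negative |
|---|---|---|
| Avoiders | 32.33% | 10.67% |
| Consumers | 14.16% | 3.96% |

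Check: 0.2 × 32.33 + 0.8 × 10.67 = 15.0; 0.2 × 14.16 + 0.8 × 3.96 = 6.0.

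**3. The planned within-stratum repeats (80% enrolment, formula of step 1).** In the example, 49.8 against 51.0 SPT-positive children give 58% power, and 199.2 against 204 SPT-negative children give 74%. Over the whole range, power is 35-74% in SPT-positives (13-32 events) and 62-83% in SPT-negatives (21-40 events).

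**4. Unadjusted against arm plus stratum (simulated Wald tests; 20,000 trials per cell for power, 40,000 for type I error).**

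| | Unadjusted | Adjusted | Gain |
|---|---|---|---|
| Power, 80% enrolment | 91.2-92.3% | 91.8-94.0% | 0.3 to 2.0 points |
| Power, 70% enrolment | 87.8-89.3% | 88.1-90.4% | −0.1 to 2.5 points |
| Type I error (10% in both arms) | 3.9-5.0% | 4.6-5.1% | |

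A separate simulation compared the unadjusted score test with the Cochran-Mantel-Haenszel test, for a share of 10-30% and an odds ratio of 1-8. It gave a gain of 0 to about 1.5 points.

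**5. Attrition.** Take the step 2 example with assumed attendance among SPT-positives of 90% in avoiders and 70% in consumers, and 80% in all SPT-negatives.

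- SPT-positive share of attending avoiders: 0.18/(0.18 + 0.64) = 0.2195. Rate: 0.2195 × 32.33 + 0.7805 × 10.67 = 15.42%.
- SPT-positive share of attending consumers: 0.14/(0.14 + 0.64) = 0.1795. Rate: 0.1795 × 14.16 + 0.8205 × 3.96 = 5.79%.
- Unadjusted difference: 15.42 − 5.79 = **9.63 points**; the true value is 9.0.
- Adjusted and standardised to the randomised mix: 0.2 × (32.33 − 14.16) + 0.8 × (10.67 − 3.96) = **9.0 points**.

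Over the step 2 range, in both directions:

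| Assumed attendance gap between arms in SPT-positives | Unadjusted difference (true 9.0) |
|---|---|
| 5 points | 8.8-9.2 |
| 10 points | 8.5-9.5 |
| 20 points | 8.1-9.9 |

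Adding a 0-20 point attendance difference between strata, and allowing the arm odds ratio to be equal or to differ two-fold between strata, widens the unadjusted range to 7.2-10.3. The arm-plus-stratum model then gives 8.1-9.9 standardised to attenders. Standardised to the LEAP ITT mix, it gives 9.0 with a common arm odds ratio and 8.6-9.4 with the two-fold difference.

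**6. Comorbidities (lesser point).** Assumed: prevalence 20-40% in avoiders, comorbidity-allergy odds ratio 2-8. If the arm does not affect the comorbidity, the adjusted risk difference stays at 9.0. With an arm odds ratio of 0.8, 0.6 or 0.4 on the comorbidity, it becomes 8.0-8.8, 6.8-8.5 or 5.2-8.2.

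**The case against.** The best counter-case is that nothing is broken. Protocol and SAP agree on a valid model, the stratum is analysed, the open covariate list would allow it, and the pooled unadjusted result stands beside the stratum results. The power gain is smaller than the spread between reasonable power formulas, which run from 88.6% to 91.4% at 80% enrolment. The attrition shift is also small against sampling error: with SE 0.0271, the 95% half-width is 1.96 × 2.71 = 5.3 points, so a shift of 0.2-0.5 points for a gap of 5-10 points is under a tenth of it. The wider figures need large assumed gaps. The LEAP ITT imputations already restore much of the randomised mix, and use each child's own earlier status. Finally, V60 and V72 results by arm are known, so changing a co-primary model now may look informed by data.

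Most of this stands as a limit on size. It does not remove the gap. An open list permits the stratum but does not pre-specify it. The imputations rest on stable status or on transition rates with no arm or stratum named, so an estimate that needs neither complements them; it does not repair them, and it fails if loss depends on more than arm and stratum. The late-change objection is a fair caution, but the stratum was set before any outcome, the unadjusted result would stay on view, and a named sensitivity analysis avoids the issue.

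**Conclusion.** The point holds as a gap in pre-specification that should be closed, not as an error in the primary test. No pooled estimate adjusted for the SPT stratum is named anywhere for this co-primary comparison. The planned power is correct. On assumed stratum inputs, adjustment gains 0.3-2.0 points of power at 80% enrolment and about 0 to 2.5 at 70%. It guards against a distortion that is small unless attendance differs markedly by arm within strata: up to 0.9 points on 9.0 for a 20-point gap, and 7.2-10.3 in the most adverse combination tried. The stratum and attendance inputs are all assumptions, because the documents give none. The comorbidity point is conditional on V144 values being used and does not carry the conclusion.

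**What to change.** 1. Pre-specify a logistic model with arm and LEAP SPT stratum, preferably as the main model. That needs the route in Protocol 9.5: "Any change in these features requires either a protocol or an SAP amendment, which is subject to review by the NIAID DSMB", and by the sponsor and the Ethics Committee. Otherwise add it to the SAP as a named sensitivity analysis, which is a short addition and leaves the primary test unchanged.
2. Report a risk difference standardised to the stratum mix of the LEAP randomised (ITT) cohort, with the unadjusted result beside it. This is needed because the adjusted odds ratio is conditional and differs slightly from the unadjusted one (0.33-0.36 against 0.36 in the simulations).
3. State the cohort and count behind that mix. Protocol 3.1 gives 640 enrolled and says: "All participants who enrolled in LEAP, including those who were not part of the intent-to-treat (ITT) population, are eligible to enroll in this study". Protocol 9.3 says: "there are 311 LEAP avoiders and 319 LEAP consumers (total 630) potentially eligible for enrollment". Protocol 1.1 uses 628 as the LEAP-On denominator. Figure 1 is not available here, so these counts cannot be reconciled.
4. In the additional models, state when each covariate is measured. Restrict allergic comorbidities to values recorded at or before LEAP randomisation where these are on file, and label any model with V144 comorbidities as exploratory.

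No new data are needed: the planned within-stratum repeats already require the stratum.

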8.2.1.2.1. Sensitivity Analysis: Imputation from LEAP On

LEAP Participants who have a missing peanut allergy determination for LEAP Trio at V144 according to the definition in section 8.2.1.1 will have their peanut allergy status from the LEAP On primary endpoint for peanut allergy status at V72 carried forward (via LOCF) as their V144 peanut allergy status.

The same statistical methodology in section 8.2.1.2 will be repeated for this sensitivity analysis to compare the rate of peanut allergy between LEAP Consumers and LEAP Avoiders at V144.

8.2.1.2.2. Sensitivity Analysis: Imputation from LEAP On with Transient Allergy Rate

LEAP Participants who have a missing peanut allergy determination for LEAP Trio at V144 according to the definition in section 8.2.1.1 will have their peanut allergy status imputed.

For the LEAP Participants with a peanut allergy status at both V72 and V144, if there are any participants whose peanut allergy status changes from V72 to V144, the percentage of participants who change from allergic to tolerant (%A72→T) and the percentage of participants who change from tolerant to allergic (%T72→A) will be calculated.

For LEAP Participants with a missing peanut allergy determination at V144 and a peanut allergy status of allergic at V72 (NumPA), [NumPA * %A72→T] participants will be randomly selected to be imputed as tolerant at V144 and the remaining participants in NumPA will be imputed as allergic at V144.

For LEAP Participants with a missing peanut allergy determination at V144 and a peanut allergy status of tolerant at V72 (NumPT), [NumPT * %T72→A] participants will be randomly selected to be imputed as allergic at V144 and the remaining participants in NumPT will be imputed as tolerant at V144.

The same statistical methodology in section 8.2.1.2 will be repeated for this sensitivity analysis to compare the rate of peanut allergy between LEAP Consumers and LEAP Avoiders at V144.

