For the LEAP Participants with a peanut allergy status at both V60 and V144, if there are any participants whose peanut allergy status changes from V60 to V144, the percentage of participants who change from allergic to tolerant (%A60→T) and the percentage of participants who change from tolerant to allergic (%T60→A) will be calculated.

For LEAP PP Participants with a missing peanut allergy determination at V144, a missing peanut allergy status at V72 and a peanut allergy status of allergic at V60 (NumPPA60), [NumPPA60 * %A60→T] participants will be randomly selected to be imputed as tolerant at V144 and the remaining participants in NumPPA60 will be imputed as allergic at V144.

For LEAP PP Participants with a missing peanut allergy determination at V144, a missing peanut allergy status at V72 and a peanut allergy status of tolerant at V60 (NumPPT60), [NumPPT60*%T60→A] participants will be randomly selected to be imputed as allergic at V144 and the remaining participants in NumPPT60 will be imputed as tolerant at V144.

The same statistical methodology in section 8.2.1.2 will be repeated for this sensitivity analysis to compare the rate of peanut allergy between LEAP Consumers and LEAP Avoiders at V144.

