8.2.1.4. Exploratory Analyses of the Primary Endpoint

Change in Peanut Allergy Status over Time

The peanut allergy status in LEAP Participants will be examined across the V60, V72 and V144 time points. Immunologic outcomes and other clinical outcomes will be summarized and plotted to explore the relationships between the change or stability in the peanut allergy status over time, as well as between the LEAP Consumers and LEAP Avoiders.

Cumulative Protective Effect

The cumulative protective effect of the LEAP Study intervention on the development of peanut allergy over time will be evaluated in LEAP Participants. LEAP Participants with a peanut allergy status of allergic at any of the time points in the LEAP Studies (V60, V72 or V144) will be considered allergic. LEAP Participants with peanut allergy status of tolerant at all time points with a determinate peanut allergy status will be considered tolerant.

The prevalence of peanut allergy across the LEAP Studies will be compared between LEAP Consumers and LEAP Avoiders using a logistic regression model in all LEAP participants in the LEAP Trio ITT sample with a determinate peanut allergy status at V144 and at least one determinate peanut allergy status at V60 or V72. The same statistical methodology will be repeated in the LEAP Participants in the LEAP Trio PP sample with a determinate peanut allergy status at V144 and at least one determinate peanut allergy status at V60 or V72

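### The transient-allergy-rate sensitivity analyses impute missing V144 status with one change rate for both arms and a single random draw, and no analysis varies the rate in missing consumers

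*SAP*

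**What the plan says.** SAP 8.2.1.1 fixes who is missing among enrolled children: those with no challenge and no qualifying intake history who also "do not have any of the assessments for the peanut allergy prediction model will not be included in the primary analyses". The primary comparison in 8.2.1.2 is therefore a complete-case logistic regression. Six sensitivity analyses follow.

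- **Carry-forward (8.2.1.2.1, .3, .5).** Children without a V144 determination "will have their peanut allergy status from the LEAP On primary endpoint for peanut allergy status at V72 carried forward (via LOCF"). In .3 and .5, V60 status is used if V72 is missing.
- **Transient allergy rate (8.2.1.2.2, .4, .6).** The rule opens "For the LEAP Participants with a peanut allergy status at both V72 and V144, if there are any participants whose peanut allergy status changes" and computes one allergic-to-tolerant and one tolerant-to-allergic percentage. Each is multiplied by the number of missing children with that earlier status, and that many "participants will be randomly selected to be imputed as tolerant at V144", or as allergic for those tolerant earlier. The V60 fallback in 8.2.1.2.4 has the same form: "For the LEAP Participants with a peanut allergy status at both V60 and V144, if there are any". Section 8.2.1.2.6 imports the method, "using the same imputation methods specified in section 8.2.1.2.4".

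Analyses .3 to .6 also cover LEAP children "or who did not participate in LEAP Trio will have the peanut allergy status at V144 imputed" (the wording in .3), so they fill in non-enrollees as well as enrolled children without a determination.

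Arm appears only in the final comparison. The PP version (.4) takes its rates from all LEAP Participants rather than the PP set. No number of imputations, combining rule, seed or rounding rule is given. Protocol 9.4 leaves missing-data methods to the SAP.

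**The concern.** Protocol 1.2 frames the study as lasting tolerance against transient desensitisation, and Protocol 9.2.1 looks for the latter in consumers. That alternative concerns change in one arm. Giving missing children in both arms the same change rate, or no change, assumes it away in the missing data. If missing consumers lose protection more often than observed ones, none of the six analyses would show it, and their agreement with the primary result could be read as robustness that was never tested.

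Other planned work helps only in part. SAP 8.2.1.3 tests change within observed consumers. SAP 8.2.1.4 looks at the relationships "between the change or stability in the peanut allergy status over time, as well as between the LEAP Consumers and LEAP Avoiders", again in observed children. SAP 6.2 compares those who did and did not join Trio by arm, on earlier data. None bounds V144 status in the missing children.

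**Working it through.** **Inputs from the documents.** V72 allergy 18.6% in avoiders and 4.8% in consumers; three new cases in each group from V60 to V72 (Protocol 1.1). 311 avoiders and 319 consumers; enrolment examples of 80% and 70%; planning rates of 15% and 6% (Protocol 9.3).

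**Assumptions.** V72-to-V144 change rates are not given. I take 5% resolution in both arms unless stated, and vary new allergy. Missing fractions of 20% / 30% come from the enrolment examples and suit .5 and .6.

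**The plan's own figure.** The pooled-variance two-proportion formula, 15% vs 6%, two-sided 0.05, gives 91.2% power with 249 and 255 children and 87.2% with 218 and 223. Protocol 9.3 states 91% and about 87%. The imputation sections state no figure.

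**What each rule imputes.** Let q be the earlier allergy rate in an arm, a the allergic-to-tolerant rate and t the tolerant-to-allergic rate. With common a and t, the imputed rate is q(1 − a) + (1 − q)t, so the imputed gap is (q_av − q_con)(1 − a − t), whichever arm changed. Carry-forward imputes q_av − q_con = 13.8 points unchanged. With similar resolution in both arms, the pooled rule overstates the persisting effect if consumers acquire allergy faster and understates it if avoiders do. Carry-forward overstates whenever the true gap has shrunk, even with equal change rates.

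**Worked case: new allergy 6% in consumers, 1% in avoiders.**

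- True V144 rates: avoiders 0.186×0.95 + 0.814×0.01 = 18.5%; consumers 0.048×0.95 + 0.952×0.06 = 10.3%. Gap 8.2, the same in complete cases.
- Pooled t = (0.01×0.814×311 + 0.06×0.952×319) / (0.814×311 + 0.952×319) = 0.037. Imputed gap 13.8×(1 − 0.05 − 0.037) = 12.6.
- Pooled rule overall: 0.8×8.2 + 0.2×12.6 = 9.1; with 30% missing, 9.5.
- Carry-forward overall: 0.8×8.2 + 0.2×13.8 = 9.3; with 30% missing, 9.9.

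Gaps in percentage points, 20% / 30% missing:

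| New allergy, consumers vs avoiders | Truth | Pooled rule | Carry-forward |
|---|---|---|---|
| 1.2% vs 1.3% (V60-V72 experience) | 13.0 | 13.0 / 13.0 | 13.2 / 13.3 |
| 7.0% vs 7.6% (the same, scaled from 12 to 72 months) | 12.6 | 12.5 / 12.5 | 12.9 / 13.0 |
| 6% vs 1% | 8.2 | 9.1 / 9.5 | 9.3 / 9.9 |
| 1.2% in both, resolution 20% | 10.9 | 10.9 / 10.9 | 11.5 / 11.8 |

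At an assumed 5% / 10% missing, the 6% vs 1% case gives 8.4 / 8.7 pooled and 8.5 / 8.8 by carry-forward.

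**Where significance is lost** (Wald test from logistic regression, expected counts, avoiders at 1%). With nobody missing, significance goes at about 8.6% new allergy in consumers (true gap 5.7 points). At 20% / 30% missing, complete-case loses it at 8.0% / 7.6%, the pooled rule only at 10.2% / 11.3%, and carry-forward at 10.8% / 12.3%.

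**Missing consumers who differ.** Put missing consumers at 10% new allergy and observed children at the V60-V72 rates. Truth is 11.4 / 10.5, while complete-case, pooled and carry-forward all give 13.0 to 13.3.

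**Tipping point, planning rates.** Hold missing avoiders at 15%. At 80% enrolment, observed 37/249 and 15/255 plus 9 of 62 missing avoiders gives p = 0.039 with 15 of 64 missing consumers allergic and 0.053 with 16. At 70%, 33/218 and 13/223 plus 14 of 93 gives 0.041 with 18 of 96 and 0.056 with 19. With unrounded expected counts the crossings are 17 of 64 and 18 of 96. So the range is 25-27% of missing consumers at 80% and 19-20% at 70%.

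**Single draw.** Over 6,000 simulations of the first and third table rows, the mean reported SE divided by the actual SD of the log odds ratio is 0.95-0.97 for the pooled rule, 0.97-0.98 with no missing data, and 0.89-0.94 for a single draw with arm-specific rates.

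**Stress case, not an expected scenario.** Effect fully gone (18.5% allergic in both arms), 4,000 simulations. False-positive rates at 20% / 30% missing: complete-case 4.6 / 5.0%, pooled single draw 12.8 / 22.4%, carry-forward 15.2 / 29.9%, arm-specific single draw 6.5 / 6.4%, arm-specific with 20 imputations 4.7 / 4.5%.

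**The case against.** Nothing decisive depends on these analyses: the primary test is complete-case, and no rule ties the conclusion to the six. On the only documented change data the bias is negligible. The 6% vs 1% split is assumed, and even there every analysis stays significant (complete-case p about 0.009 / 0.015, pooled about 0.001). Few enrolled children should lack a status, given home visits, telephone visits and home blood collection, so .1 and .2 barely move; the PP set size behind .3 and .4 is not given. Pooling is defensible because only about 13 consumers (13 of 270) were allergic at V72. If missingness is unrelated to earlier status, the complete-case analysis already treats missing consumers like observed ones. The single draw is inferred from silence and costs little under the pooled rule. The tipping points lie far above 4.8% or 6%, which itself suggests robustness.

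Most of this stands, and it sets the weight of the point. It does not remove the gap. The V60-V72 interval covers one year, while V144 asks about roughly six more. The reassuring tipping-point figures come from this review at planning rates, not from any analysis the SAP would produce on the data.

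**Conclusion.** The point holds as a robustness gap, not an error in the primary result. As written, the change rates are not split by arm, the draw is single, and nothing varies the rate in missing consumers. The resulting bias runs from nil, when change is similar in both arms, to about 1 point of gap at 6% vs 1% new allergy with 20-30% missing; it reverses if avoiders change faster. It matters mainly for 8.2.1.2.5 and .6, which impute non-enrollees. All V72-to-V144 change rates here are assumptions, and the missing fractions are the protocol's enrolment examples rather than forecasts. The reading that rates are pooled is the plain one, but a single phrase could show otherwise. The single draw is minor alone and becomes relevant once rates are split by arm. This is a change worth considering.

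**What to change.** 1. In 8.2.1.2.2, .4 and .6, state that change rates are computed within randomised arm, and within the PP set for .4. Pool arms only for the sparse consumer allergic-to-tolerant rate.
2. Replace the single selection with multiple imputation (for example 20 imputations, rates redrawn each time), with a stated seed and combined variance.
3. Add one tipping-point analysis on the .5/.6 population. Hold missing avoiders at the observed avoider rate, raise new allergy among missing consumers until p exceeds 0.05, and report that count and percentage.
4. Label .1, .3 and .5 as assuming no change since V72 or V60.

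Items 1 and 2 repair the imputation if data are missing at random given arm and earlier status. Only item 3 addresses missing consumers who differ from observed ones, so it is the one to keep if only one is adopted. The cost is a few SAP sentences and a short program, with no new data. The drawback is that the consumer allergic-to-tolerant rate stays imprecise or must borrow from avoiders.
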